**Table 14: Recommended Turalio® and Sirolimus Dose Modifications**

Dose interruptions for Grade 2 non-hematologic toxicity for up to 1 week can be implemented at the discretion of the treating physician to manage intolerable or clinically significant toxicity. No dose reduction is required when resuming treatment (unless hepatotoxicity).

## **9. ADVERSE EVENTS: LIST AND REPORTING REQUIREMENTS**

### **9.1 Adverse Events Most Likely Related to Turalio® and Sirolimus**

#### **9.1.1 Turalio®**

For a complete adverse event profile, please refer to IB version 12. Side effects that may be seen with Turalio® given by itself or in combination with other anti-cancer treatments.

Common side effects ( $\geq 10\%$  by frequency) associated with the use of Turalio® include the following:

- Nausea
- Vomiting
- Constipation
- Abdominal pain
- Abnormal, altered, or loss of sense of taste
- Decreased appetite
- Rash
- Pruritus (itching of skin)
- Hair color changes (to white or gray; original color usually returns after stopping study drug)
- Increases in liver blood tests
- Fatigue or tiredness
- Headache (including migraine)
- Hypertension (high blood pressure)
- Edema (swelling of tissues in limbs or face)
- Eye edema (swelling in or around the eyes)

Less common side effects (less than 10%) associated with the use of Turalio® include the following:

- Hepatotoxicity (liver injury), which may be serious and fatal
- Cognitive disorder (includes memory impairment, amnesia, cognitive disorder, attention deficit hyperactivity disorder, disturbance in attention)
- Dry mouth
- Neuropathy (numbness or weakness)
- Stomatitis (inflammation inside of mouth, usually a small sore or ulcer)
- Alopecia (loss of hair)
- Skin color changes
- Pyrexia (fever)
- Vision changes (including blurred vision, sensitivity to light, double vision, and reduced visual clarity)
- Increase in bilirubin (produced when the liver breaks down red blood cells)
- Decrease in white blood cell counts (which could include one or more of the following: white blood cell counts, lymphocytes, neutrophils, leukocytes; this may lead to increased risk of infection)
- High cholesterol

**Turalio® may cause liver injury, also known as hepatotoxicity. Such an injury can be severe and prolonged despite stopping of study medication. The liver injury may be fatal.** Should your liver tests become abnormal you may be required to have additional monitoring and evaluation, which may include a liver biopsy. Treatment may include blood filtering to remove waste products of the liver. One patient required a liver transplant. One patient died before the liver injury got better. Taking Turalio® together with other medications may increase the risk of severe liver injury.

Turalio® . This type of rash may sometimes include fever and inflammation of internal organs.

Animals treated with Turalio® showed decrease in the pumping action (contraction) of the heart. There have been two reports of reduced ejection fraction (the amount of blood pumped by your heart with each beat) in patients receiving Turalio® at a dose of 3000 mg/day, a much higher dose than you will receive. The role of Turalio® in these events is undetermined at this time.

The severity of the side effects listed above could range from mild to severe or even life-threatening. In addition, there may be other risks or side effects from Turalio® that are not listed above or unknown at this time. It is also possible to experience a serious allergic reaction, which could become life-threatening or fatal. Symptoms of an allergic reaction include rash, hives, itching, swelling of the mouth, face, lips or tongue, dizziness, low blood pressure, tightness in the chest, or trouble breathing.

#### **Reproductive Risks**

If a patient or partner becomes pregnant or fathers a child while in this research study or 90 days following study completion, they must notify the study doctor immediately. The risk of taking this product in pregnant women has not been fully determined from either human studies or animal studies. There is no clinical experience in humans with Turalio® in pregnant or lactating women.

Turalio® can cause fetal defects in rodents and rabbits, and should be considered potentially harmful to the human fetus, with the potential to cause fetal malformations. As a result, Turalio® should not be administered to pregnant women or lactating women who are breastfeeding. Patients and partners should avoid becoming pregnant over the course of this study. Becoming pregnant while participating in the study will expose the patient or partner to a potential loss of the pregnancy, or other unknown effects on an unborn child such as, but not limited to, birth defects and premature delivery. They will be withdrawn from the study if they become pregnant or have a positive pregnancy test. If they become pregnant, they will be followed until the time the pregnancy is completed or terminated in order to collect information about the pregnancy, determine the outcome of the pregnancy, childbirth and the health of the baby (first well-baby visit). If the pregnancy continues to term, the outcome (health of infant) must also be reported. All pregnancy/lactation reports, including pregnancy reports in which the patient or a partner of a patient may have been exposed to the Product(s) via either maternal or paternal exposure, lactation reports, unintended pregnancy, with or without an associated adverse event, where the fetus could have been exposed to the study drug shall be collected.

In animal studies, Turalio® caused a decrease in sperm count and changes in the ovaries which were reversible at the end of the study. Turalio® may therefore affect fertility in both men and women. If you are a male, you may ask your study doctor about sperm banking.

#### **9.1.2 Sirolimus**

Sirolimus is approved for prophylaxis of organ rejection in patients receiving renal transplants. Known toxicities include risk of opportunistic infections, interstitial lung disease, hyperlipidemia, risk of malignancy (including lymphoma), proteinuria, mucositis, nausea, emesis, diarrhea, edema, elevated liver enzymes, and bone marrow suppression including anemia, neutropenia, and thrombocytopenia.

Side effects that may be seen with Sirolimus given by itself or in combination with other anti-cancer treatments.

Some common side effects ( $\geq 30\%$  by frequency) seen with the use of Sirolimus in patients with cancer include the following:

- Peripheral edema
- Hypertriglyceridemia
- Hypercholesterolemia
- Increased creatinine (kidney dysfunction)
- Hypertension (an increase in blood pressure)
- Nausea
- Abdominal pain
- Diarrhea
- Constipation
- Headache
- Fever
- Urinary tract infection

**Columbia University Medical Center**  
**Herbert Irving Comprehensive Cancer Center**  
**Version Date: 04/21/2021**

- Anemia
- Thrombocytopenia
- Arthralgia
- Peeling of the skin over large areas of the body
- Swelling just below the surface of the skin, most often around the lips and eyes
- Hypersensitivity

Other side effects that are less common (3% to less than 20%):

- Sepsis
- Pneumonia (lung infection)
- Pyelonephritis (kidney infection)
- Virus infection (herpes zoster, herpes simplex)
- Venous thromboembolism (pulmonary embolism, deep venous thrombosis)
- Tachycardia
- Stomatitis
- Thrombotic thrombocytopenic purpura/hemolytic uremic syndrome
- Hemolytic uremic syndrome (a kidney condition where destroyed red blood cells block kidney filtering abilities.
- Leukopenia
- Abnormal healing
- Increased lactic dehydrogenase (LDH)
- Hypokalemia
- Bone necrosis
- Epistaxis (nose bleed)
- Skin cancers (including melanoma, squamous cell carcinoma, and basal cell carcinoma)

Other side effects that are possible, some may be serious include:

- Hepatotoxicity (liver dysfunction), including fatal hepatic necrosis, with elevated Sirolimus trough concentrations
- Pericardial effusion (fluid around the heart that may require an intervention)
- Progressive multifocal leukoencephalopathy (PML)
- Lung disease (including pulmonary fibrosis and pulmonary hemorrhage)
- Nephrotic syndrome and kidney dysfunction
- Azoospermia (lack of sperm production) which is reversible after discontinuation of Sirolimus

Taking Sirolimus together with other medications that can cause liver function abnormalities may further increase the risk of severe liver injury.

## Study Drugs

### **9.6 Drug Descriptions**

#### **9.6.1 Turalio® Description**

Turalio® will be supplied in 200mg capsules and should be taken twice daily as split doses approximately 12 hours apart. Each dose should be taken with approximately 8 ounces of water. Subject should fast for at least two hours before and one hour after dosage. Each cycle of treatment will last 28 days. Turalio® should not be taken with medications that may decrease the acid content of the stomach as it may affect drug absorption.

The dose level for the phase 2 portion of the study was determined to be dose level 3 (Turalio® should be taken 400mg orally in AM and 600mg in PM daily in combination with Sirolimus 2mg orally daily in AM in a fasting state).

#### **Sirolimus Description**

Sirolimus will be supplied in 0.5mg, 1.0mg, or 2.0mg tablets and should be taken once daily (in AM) approximately 24 hours apart. Each dose should be taken with approximately 8 ounces of water when taking the AM dose of Turalio®. Subject should fast for at least two hours before and one hour after dosage. Each cycle of treatment will last 28 days.

### **9.7 Treatment Regimen**

Turalio® and Sirolimus are oral tablets and are intended for continuous outpatient administration in 28 day cycles until criteria for ending the study have been met. Both drugs are to be taken two hours before or after a meal or snack.

Turalio® is to be taken twice daily. Sirolimus is to be taken once daily. The drugs can be taken at the same time. Dose levels tested in the phase 1 portion of the study are indicated in Table 1, Section 5.1.

The phase 1 study was executed as an open-label, continual reassessment method dosing of Turalio® and Sirolimus which began enrollment with a Turalio® dose of 800 mg per day, i.e., 400 mg PO AM and 400mg PO PM along with Sirolimus 2mg PO daily in AM. Dose escalation groups were as described in Section 4.1.

Review of the phase 1 safety data was assessed by the continual reassessment method and identified dose level 3 (Turalio® 1000mg in combination with Sirolimus 2mg) to be the recommended phase 2 dose. For dose modification guidelines for the phase 2 portion of the study, please refer to section 8.2 and Tables 10 – 14 above.

## **11. MEASUREMENT OF EFFECT**

### **11.1 Antitumor Effect – Solid Tumors**

For the purposes of this study, patients should be re-evaluated for response every six weeks within the first 36 weeks. In addition to a baseline scan, confirmatory scans should also be obtained six weeks following initial documentation of objective response.

Response and progression will be evaluated in this study using the new international criteria proposed by the revised Response Evaluation Criteria in Solid Tumors (RECIST) guideline (version 1.1) [Eur J Ca 45:228-247, 2009]. Changes in the largest diameter (unidimensional measurement) of the tumor lesions and the shortest diameter in the case of malignant lymph nodes are used in the RECIST criteria. Therapy may be permitted beyond progression if patient is deriving clinical benefit after initial tumor growth or ambiguity regarding the existence of disease progression in consultation with the principle investigator, sponsor, and central IRB. If subsequent imaging confirms tumor growth, progression will be back dated to the prior scan. If patient agrees to treatment beyond progression, the patient will be required to sign a “Treatment Beyond Progression” informed consent form.

#### **11.1.1 Definitions**

Evaluable for toxicity: All patients will be evaluable for toxicity from the time of their first treatment with Turalio® and Sirolimus.

Evaluable for objective response: Only those patients who have measurable disease present at baseline, have received at least one cycle of therapy, and have had their disease re-evaluated will be considered evaluable for response. These patients will have their response classified according to the definitions stated below. (Note: Patients who exhibit objective disease progression prior to the end of cycle 1 will also be considered evaluable.)

Evaluable Non-Target Disease Response: Patients who have lesions present at baseline that are evaluable but do not meet the definitions of measurable disease, have received at least one cycle of therapy, and have had their disease re-evaluated will be considered evaluable for non-target disease. The response assessment is based on the presence, absence, or unequivocal progression of the lesions.

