The primary outcome measure is progression free survival (PFS) in patients with MPNST at the recommended dose determined from the Phase 1 study, Dose level 3 (1000mg of Turalio® orally total daily in combination with 2mg of Sirolimus orally once daily). Progression free survival is defined as the time from the start of treatment until disease progression or death from any cause. Patients who have not progressed will be censored at the date of their last follow-up. Patients will be evaluated weekly for the first three weeks, at least every other week during the first two cycles and then at the beginning of every subsequent cycle. Tumor response will be assessed by CT scans performed every six weeks for the first six months, every eight weeks for the following six months, and then every 12 weeks thereafter using Response Evaluation Criteria in Solid Tumors (RECIST) 1.1. Assuming a median PFS of 6 weeks in patient treated with the standard of care (23), with a sample size of 25, we have 90% power to detect a difference of 12 weeks in median PFS (6 weeks versus 18 weeks) given a 2-sided test with an alpha of 0.05.

Patients will be required to obtain research-specific biopsies as follows:

- 1) Baseline biopsy of a target lesion
- 2) Repeat biopsy during last week of cycle 1 for pharmacodynamic analysis
- 3) Optional biopsies at time of progression

All biopsies will attempt to obtain 4-5 cores. Two of the cores will be processed for formalin fixation and 2-3 will be frozen in liquid nitrogen for exploratory analyses.

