5.1.4. ECOG performance status

0, 1, or 2

5.1.5. Age greater or equal to 18 years. Because no dosing or adverse event data are currently available on the use of Turalio® in combination with Sirolimus in patients <18 years of age, children are excluded from this study, but will be eligible for future pediatric trials.

5.1.6. Presence of measurable lesions by Response Evaluation Criteria in Solid Tumors (RECIST) v1.1

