## **8.2 Phase 2 Dose Modification**

Patients may have dose modifications at any time. Patients may have either drug held for any reason for up to 21 days before discontinuing study treatment. Refer to Tables 10 – 14 below for specific dose modification instructions.

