### **11.3 Methods for Evaluation of Measurable Disease**

All measurements should be taken and recorded in metric notation using a ruler or calipers. All baseline evaluations should be performed as closely as possible to the beginning of treatment and never more than 4 weeks before the beginning of the treatment.

The same method of assessment and the same technique should be used to characterize each identified and reported lesion at baseline and during follow-up. Imaging-based evaluation is preferred to evaluation by clinical examination unless the lesion(s) being followed cannot be imaged but are assessable by clinical exam.

**Clinical lesions:** Clinical lesions will only be considered measurable when they are superficial (e.g., skin nodules and palpable lymph nodes) and  $\geq 10$  mm diameter as assessed using calipers (e.g., skin nodules). In the case of skin lesions, documentation by color photography, including a ruler to estimate the size of the lesion, is recommended.

**Chest x-ray:** Lesions on chest x-ray are acceptable as measurable lesions when they are clearly defined and surrounded by aerated lung. However, CT is preferable.

**Conventional CT and MRI:** This guideline has defined measurability of lesions on CT scan based on the assumption that CT slice thickness is 5 mm or less. If CT scans have slice thickness greater than 5 mm, the minimum size for a measurable lesion should be twice the slice thickness. MRI is also acceptable in certain situations (e.g., for body scans).

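### No ORR denominator is named in the text reviewed; if the response-evaluable set in Section 11.1.1 serves, treated patients lost early without documented progression drop out and ORR tends to be too high

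*Combined protocol and SAP*

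**What the plan says.** ORR by RECIST 1.1 is a secondary Phase 2 endpoint (Sections 1.2 and 13.1). The secondary analysis in Section 13.3 gives the method, a proportion with an exact 95% confidence interval, and no analysis set.

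Section 11.1.1 defines who is evaluable for objective response: only patients with measurable disease at baseline who "have received at least one cycle of therapy, and have had their disease re-evaluated will be considered evaluable for response". A note adds: "Patients who exhibit objective disease progression prior to the end of cycle 1 will also be considered evaluable". For toxicity the same section is inclusive: "All patients will be evaluable for toxicity from the time of their first treatment". Its other response definition, for non-target disease, carries the same cycle and re-evaluation conditions. It should not apply here, because Section 5.1.6 makes this an entry criterion: "Presence of measurable lesions by Response Evaluation Criteria in Solid Tumors (RECIST) v1.1".

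On timing, Section 9.7 describes "continuous outpatient administration in 28 day cycles", and the Phase 2 part of Section 4.1 states: "Tumor response will be assessed by CT scans performed every six weeks for the first six months".

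On early stopping, the note under the response table in Section 11.4.3 foresees patients who deteriorate and stop without objective progression, and asks that progression still be documented afterwards if possible. Section 7.5 asks for end-of-study procedures within 28 days of stopping. It allows discretionary replacement of some withdrawn patients, but not those withdrawn for toxicity or clinically significant progression. Section 13.1 plans 25 evaluable Phase 2 patients without saying what they must be evaluable for.

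**The concern.** Two of the three conditions in Section 11.1.1 are met or failed only after treatment starts. A denominator built on them is selected by early outcome, and the patients most likely to fail them are those doing badly: early deaths, early toxicity stops, and clinical deterioration without a scan. The reported ORR would then describe patients who got through early treatment, not everyone who started it.

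In a single-arm study of 25 patients, the ORR is likely to be set beside rates from other studies, so the denominator matters to the reader. If it is left open, it can also be settled after the responses are known.

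**Working it through.** The plan states no ORR target, precision or expected rate, so there is no figure to reproduce. The check first asks who is left out, then how far the rate moves.

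**Who is left out under Section 11.1.1**

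- *Measurable disease at baseline.* Already required for entry, so it removes no eligible patient.
- *Disease re-evaluated.* Removes every treated patient with no post-baseline assessment, for example after early death, a toxicity stop, or deterioration without objective progression (group 1).
- *At least one cycle received.* Removes patients who stop for good before completing 28 days without objective progression by then, even if they are scanned later (group 2). This group is narrow, because Section 8.2 says: "Patients may have either drug held for any reason for up to 21 days before discontinuing study treatment". A hold within cycle 1 does not by itself end treatment.
- *The note on early progression.* Keeps patients with objective progression before the end of cycle 1, that is, by day 28. The first scheduled CT is at week 6 = day 42. The note therefore depends on an unscheduled scan or on clinical measurement, and Section 11.3 restricts the latter: "Clinical lesions will only be considered measurable when they are superficial".
- Patients who complete a cycle and progress at the week-6 scan stay in.

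**How far the rate moves**

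Inputs: 25 Phase 2 patients (Sections 4.3 and 13.1). The number of excluded non-responders, k, and the number of responders, x, are assumptions, because the documents give neither. I take k = 1, 3, 5 and x = 1, 3, 5.

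All-treated rate = x/25. Response-evaluable rate = x/(25 − k). Ratio = 25/(25 − k):

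- k = 1: 25/24 = 1.042
- k = 3: 25/22 = 1.136
- k = 5: 25/20 = 1.250

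Rates with exact (Clopper-Pearson) 95% intervals:

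| Responders | All 25 treated | k = 1 (n = 24) | k = 3 (n = 22) | k = 5 (n = 20) |
|---|---|---|---|---|
| 1 | 4.0% (0.1–20.4) | 4.2% (0.1–21.1) | 4.5% (0.1–22.8) | 5.0% (0.1–24.9) |
| 3 | 12.0% (2.5–31.2) | 12.5% (2.7–32.4) | 13.6% (2.9–34.9) | 15.0% (3.2–37.9) |
| 5 | 20.0% (6.8–40.7) | 20.8% (7.1–42.2) | 22.7% (7.8–45.4) | 25.0% (8.7–49.1) |

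Largest shift: 25.0 − 20.0 = 5.0 points. Interval widths at n = 25: 31.2 − 2.5 = 28.7 points with 3 responders and 40.7 − 6.8 = 33.9 points with 5. With no responders the estimate stays at 0%, and only the upper limit moves, from 13.7% (n = 25) to 16.8% (n = 20).

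**Direction**

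A group 1 patient has no assessment and cannot be a responder. Removing such patients shrinks the denominator only, so ORR stays the same or rises. A group 2 patient scanned later could be a responder. If the one excluded patient were a responder, the reported rate would be 3/24 = 12.5% against 4/25 = 16.0% in all treated, a shift downward.

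**The case against.** The strongest reply is that nothing shows the Section 11.1.1 set will be the ORR denominator. It sits under measurement of effect, not statistics, and can be read as saying only whose response gets classified. Section 13.3 does not refer to it. The public text also runs from Section 13.1 to 13.3, and the response sentence lacks its week number, so a denominator could be stated where it cannot be seen. This stands as a limit: the point concerns the text reviewed and is conditional on that set being used. It does not remove the point, because the set is labelled as the one for objective response and no other applicable set is given.

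Second, follow-up after stopping may shrink the excluded groups. The end-of-study procedures in Section 7.5 may include imaging, though the schedule was not available to check, and the Section 11.4.3 note asks for progression to be documented after discontinuation. Both may reduce losses. Neither says how a patient who remains unassessed is counted.

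Third, the larger scenarios may be generous. Nothing in the documents supports k = 5, and Section 2 cites a 1.3% tumour response with an mTOR inhibitor and no appreciable response to targeted monotherapies. With one responder, even k = 5 moves ORR only from 4.0% to 5.0%. This is fair.

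A reader might also take the PFS medians as a guide to k. Under exponential PFS, 1 − 2^(−6/18) = 21% of patients (18-week median) or 1 − 2^(−6/6) = 50% (6-week median) have an event by week 6. These are not estimates of k, because patients with objectively documented progression are generally kept.

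**Conclusion.** The point holds as a conditional and modest one. In the text reviewed, ORR has no stated denominator, and the only applicable response set is selected on events after treatment starts. If that set is used, ORR is inflated by a factor of 1.04 to 1.25 for 1 to 5 excluded non-responders out of 25 treated, at most 5.0 points in the cases shown. This rests on assumed values of k and x and on the excluded patients being non-responders. The shift is small against the sampling uncertainty, although the interval does not account for selective exclusion. It is zero if nobody is excluded or nobody responds.

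Three stronger readings are not supported:

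- *That ORR must be biased upward.* The direction is certain only for patients never re-evaluated. For those scanned after an early stop it is likely, not certain.
- *That enrolment will continue until 25 patients are response-evaluable.* Section 7.5 does not offer replacement for toxicity or clinically significant progression, the reasons behind many of these losses.
- *That the main efficacy conclusion is at risk.* ORR has no target or decision rule, and PFS does not use the response-evaluable definition.

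**What to change.** In Sections 11.1.1 and 13.3, make the main ORR denominator all Phase 2 patients who received at least one dose. Count patients with no post-baseline tumour assessment as non-responders, and classify those scanned after an early stop by their scans. Keep the response-evaluable ORR as a supportive analysis, with the number excluded and the reasons. In Section 13.1, say what evaluable means for the 25 patients, consistently with the replacement text in Section 7.5. Settle this before the responses are analysed.

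The cost is wording only, with no new patients or data. The reported ORR may be slightly lower.
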